6.2. Appendix 2: Demographics and Baseline Characteristics

Table 12 presents a list of the demographic and baseline variables that will be summarized by intervention group, combined active intervention group, and overall, for the following analysis sets: FAS.

Table 12: Demographic Variables

Continuous Variables:	Summary Type			
Age (years)	Di-4i4-4i-4i (NI			
Weight (kg)	Descriptive statistics (N, mean, SD, median and range [minimum]			
Height (cm)	and maximum], and IQ range).			
Body Mass Index (BMI) (kg/m²)	and maximum, and iQ range).			
Categorical Variables				
Age (45 years, 45-<65 years, >=65 years)				
Sex (male, female, undifferentiated)				
Race ^a (American Indian or Alaska Native, Asian, Black or African	Frequency distribution with the			
American, Native Hawaiian or other Pacific Islander, White, Multiple)	number and percentage of			
Ethnicity (Hispanic or Latino, not Hispanic or Latino)	participants in each category.			
Weight (≤90kg, >90kg)	participants in each category.			
BMI (underweight <18.5 kg/m², normal 18.5-<25 kg/m², overweight				
$25 - 30 \text{ kg/m}^2$, obese >= 30 kg/m^2)				

^aIf multiple race categories are indicated, the Race is recorded as 'Multiple'

The baseline characteristics will be summarized for the same analysis sets as the demographic variables. They include, but are not limited to, baseline disease characteristics of PsA (eg, duration of disease, PsA subtypes, baseline efficacy assessments), medical history (Appendix 5), prior exposure to non-biologic medications, prior joint procedures/injections, and baseline medication usage for PsA (Appendix 4).

6.3. Appendix 3: Protocol Deviations

In general, the following list of major protocol deviations may have the potential to impact participants' rights, safety or well-being, or the integrity and/or result of the clinical study. Participants with major protocol deviations will be identified prior to database lock and the participants with major protocol deviations will be summarized by category.

- Developed withdrawal criteria but not withdrawn
- Entered but did not satisfy criteria
- Received a disallowed concomitant treatment
- Received wrong treatment or incorrect dose
- Other

The study selection criteria will be grouped into the following 5 categories: PsA disease criteria, medication criteria, laboratory criteria, medical history criteria, and other.

Protocol deviation in study intervention administrations includes missing doses, incorrect doses, and treatments administered out of the dosing windows defined in Section 5.1.1.1. Additionally, missed doses due to Major Disruption or Natural Disaster will be summarized.

6.4. Appendix 4: Prior and Concomitant Medications

Prior and Concomitant medications will be coded using the [World Health Organization Drug Dictionary (WHO-DD)]. Prior medications are defined as any therapy used before the day of first dose (partial or complete) of study intervention. Concomitant medications are defined as any therapy used on or after the same day as the first dose of study intervention, including those that started before and continue on after the first dose of study intervention.

Summaries of concomitant medications will be presented by ATC class and ATC term, intervention group. The proportion of participants who receive each concomitant medication will be summarized as well as the proportion of participants who receive at least 1 concomitant medication. In addition, concomitant medications of special interest will be presented. These include non-biologic DMARDs, systemic corticosteroids, and NSAIDs. See Section 6.8 for list of medications in each category.

Prior medications taken for PsA and/or psoriasis (eg, non-biologic DMARDs, apremilast, immunosuppressives, and NSAIDS) will be summarized by randomized intervention group.

6.5. Appendix 5: Medical History

Number and percentage of participants who had medical histories of interest for PsA will be collected and summarized by intervention group, including:

- Degenerative disk disease
- Gout
- Fibromyalgia
- Inflammatory Back Pain
- Osteoarthritis
- Angina Pectoris
- Coronary Artery Bypass Graft
- Coronary Artery Disease
- Diabetes Mellitus
- Family history of early coronary artery disease less than 55
- Hyperlipidemia
- Hypertension
- Myocardial Infarction
- Percutaneous Coronary Intervention
- Peripheral Vascular Disease
- Stroke
- Transient Ischemic Attack
- Asthma
- Chronic Liver Disease (eg fatty liver, alcohol-induced, cirrhosis)
- Hidradenitis Suppurativa
- Inflammatory Bowel Disease
- Uveitis
- Squamous Cell Carcinoma
- Basal Cell carcinoma
- Other malignancy
- Family history of cancer in a 1st degree relative (not Squamous Cell or Basal Cell Carcinoma)
- Anxiety
- Depression
- COVID-19

- Hospitalized within the past year (excluding pregnancy)
- Hospitalized within the past year for infection

6.6. Appendix 6: Intervention Compliance

Compliance will be summarized descriptively for the overall study intervention, as well as for guselkumab and placebo separately. Compliance to randomized intervention versus actual intervention will be presented in a summary table and will be calculated as (the number of injections completed / the number of injections planned * 100).

6.7. Appendix 7: Adverse Events of Special Interest

Adverse events of special interest, as well as other adverse events of interest, will be identified based on criteria specified in the following table.

Type of Adverse Event	MedDRA Terms Search Methodology	Requires Medical Review	
Adverse Events of Special Interest	 		
Malignancy	Malignant tumors (SMQ-narrow scope).	Yes	
Active Tuberculosis	HLT of Tuberculosis infections excluding PT of Latent Tuberculosis	Yes	
Other Adverse Events of Interest	.		
Infections	SOC Infections and infestations Note that serious infections, and infections requiring oral or parenteral anti-microbial treatment, are based on this MedDRA determination as well as eCRF checkboxes for serious AE and for requiring oral or parenteral	No	
Opportunistic Infections	anti-microbial treatment respectively Opportunistic infections (SMQ-narrow scope)	Yes	
ISR	No MedDRA search used. Based completely on eCRF checkbox	No	
Anaphylaxis and Hypersensitivity	PTs of Anaphylactic reaction, Anaphylactic shock, Anaphylactoid reaction, Anaphylactoid shock, and Type I Hypersensitivity	No	
Serum Sickness Reactions	PTs of serum sickness and Serum sickness-like reaction	No	
MACE	Myocardial infarction (narrow) Ischaemic central nervous system vascular conditions (narrow scope) Haemorrhagic central nervous system vascular conditions (narrow scope) PTs: Sudden death AESOC:	Yes	

	Cardiac Disorders (fatal events only)	
	Vascular Disorders (fatal events only)	
	Customized MedDRA PTs related to venous thrombosis and embolism involving the deep venous vasculature:	No
VTEs	Axillary vein thrombosis, Brachiocephalic vein thrombosis, Budd-Chiari syndrome, Deep vein thrombosis, Deep vein thrombosis postoperative, Embolism venous, Hepatic vein thrombosis, Homans' sign positive, Inferior vena cava syndrome, Jugular vein thrombosis, Mahler sign, May-Thurner syndrome, Mesenteric vein thrombosis, Obstetrical pulmonary embolism, Ovarian vein thrombosis, Paget-Schroetter syndrome, Pelvic venous thrombosis, Penile vein thrombosis, Peripheral vein thrombosis, Post procedural pulmonary embolism, Postpartum venous thrombosis, Pulmonary embolism, Pulmonary infarction, Pulmonary microemboli, Pulmonary thrombosis, Pulmonary venous thrombosis, Renal vein thrombosis, Spermatic vein thrombosis, Splenic vein thrombosis, Subclavian vein embolism, Subclavian vein thrombosis corpora cavernosa, Vena cava embolism, Vena cava thrombosis in pregnancy, Venous thrombosis limb, Visceral venous	
	thrombosis	
Clinically Important Hepatic Disorders	Drug related hepatic disorders - comprehensive search (SMQ – narrow scope) and either SAE or AE leading to discontinuation of study intervention	No

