7. DISCONTINUATION OF STUDY INTERVENTION AND PARTICIPANT DISCONTINUATION/WITHDRAWAL

7.1. Discontinuation of Study Intervention

A participant's study intervention must be discontinued if:

- The participant withdraws consent to receive study intervention.
- The investigator believes that for safety reasons or tolerability reasons (eg, AE) it is in the best interest of the participant to discontinue study intervention.
- The participant becomes pregnant or plans to come pregnant within the study period. Refer to Appendix 10.7.
- A systemic opportunistic infection.
- The participant is unable to adhere to the study visit schedule or comply with protocol requirements.
- The participant is deemed ineligible according to the following TB screening criteria:
 - A diagnosis of active TB is made.
 - A participant has symptoms suggestive of active TB based on follow-up assessment questions and/or physical examination or has had recent close contact with a person with active TB, and cannot or will not continue to undergo additional evaluation.
 - A participant undergoing evaluation has a chest radiograph with evidence of current active TB and/or a positive QuantiFERON-TB test result, and/or 2 indeterminate QuantiFERON-TB test results on repeat testing (refer to Section 8.2.12.) (and/or a positive tuberculin skin test result in countries in which the QuantiFERON-TB test is not approved/registered or the tuberculin skin test is mandated by local health authorities).

Note: In Ukraine, while the QuantiFERON-TB test is not approved/registered, it is acceptable, and an additional tuberculin skin test is not required.

The frequency of TB testing can be increased depending on local health authority requirements.

- A participant receiving treatment for latent TB discontinues this treatment prematurely or is noncompliant with the therapy.
- The participant has a serious adverse reaction that is temporally related to an injection including a hypersensitivity reaction resulting in bronchospasm, wheezing and/or dyspnea that requires ventilatory support OR that results in symptomatic hypotension with a decrease in systolic blood pressure of 30% from a participant's baseline value or systolic blood pressure <90 mm Hg (Sampson, 2006). In general, discontinuation of study intervention administration must be considered for participants who develop a severe injection-site reaction.

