8.2.10. Hypersensitivity Reactions

Before any administration of study intervention at the study site, appropriately trained personnel and medications (eg, antihistamines, injectable epinephrine) must be available to treat hypersensitivity reactions, including anaphylaxis. All participants must be observed carefully for signs and symptoms of a hypersensitivity reaction (eg, urticaria, pruritus, angioedema, wheezing, dyspnea, or hypotension).

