5.4.3. Adverse Events

The verbatim terms used in the eCRF by investigators to identify AEs will be coded using the Medical Dictionary for Regulatory Activities (MedDRA). Any AE occurring at or after the initial administration of study intervention and those AEs that were present at baseline but worsened in severity after the start of initial study intervention are considered to be treatment emergent. If the event occurs on the day of the initial administration of study intervention, and either event time or time of administration are missing, then the event will be assumed to be treatment emergent. If the event date is recorded as partial or completely missing, then the event will be considered to be treatment emergent unless it is known to be prior to the first administration of study intervention based on partial onset date or resolution date. All reported treatment-emergent adverse events will be included in the analysis. For each adverse event, the number and percentage of participants who experience at least 1 occurrence of the given event will be summarized by intervention group.

Summary tables will be provided for treatment-emergent adverse events:

- Treatment emergent adverse events (TEAEs)
- Treatment emergent SAEs
- TEAEs with severe intensity
- TEAEs leading to permanent discontinuation of study intervention
- TEAEs reasonably related to study intervention
- SAEs reasonably related to study intervention

- TEAEs leading to dose interruption of study intervention
- Treatment emergent infections
- Treatment emergent serious infections
- Treatment emergent infections requiring oral or parenteral anti-microbial treatment
- Injection-site reactions
- Venous thromboembolism (VTE) events
- Clinically important hepatic disorder events
- Anaphylaxis, hypersensitivity and serum sickness reactions
- TEAEs leading to death

All AE summary tables will include average weeks of follow-up and average number of study intervention for each intervention group.

In addition to the summary tables, listings will be provided for participants who had:

- SAEs
- TEAEs leading to permanent discontinuation of study intervention
- Anaphylactic reactions or serum sickness reactions
- Malignancies
- Serious infections including TB
- TEAEs leading to death
- Venous thromboembolism (VTE) events
- Major adverse cardiovascular events (MACE) events
- Clinically important hepatic disorder events
- Opportunistic infections

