Section 6.7 contains the methods of identification for selected AEs of interest.

A listing of participants who died will be provided, including cause of death, date of death, relationship to study intervention, and study day of death in relation to reference date.

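### The adverse event summary labelled as covering hypersensitivity counts only five preferred terms, so reactions coded to any other term are left out of that count

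*SAP*

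**What the plan says.** SAP Section 5.4.3 lists the planned summary tables of treatment-emergent adverse events. One of them is "Anaphylaxis, hypersensitivity and serum sickness reactions". The same section then tells the reader where the event definitions are: "Section 6.7 contains the methods of identification for selected AEs of interest".

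Section 6.7 (Appendix 7) states that the events "will be identified based on criteria specified in the following table". In that table the anaphylaxis and hypersensitivity row, which sits outside the special-interest group, is defined as "PTs of Anaphylactic reaction, Anaphylactic shock, Anaphylactoid reaction, Anaphylactoid shock, and Type I Hypersensitivity", with medical review marked No. The serum sickness row, which feeds the same summary, is "PTs of serum sickness and Serum sickness-like reaction", also without medical review.

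The matching participant listing in Section 5.4.3 is narrower than the summary: "Anaphylactic reactions or serum sickness reactions".

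The protocol uses hypersensitivity in a wider sense. Table 1 names hypersensitivity reactions, with serious ones as a subset, among the potential risks of guselkumab. The synopsis includes them among the safety items to be collected. Section 8.2.10 asks sites to watch for "signs and symptoms of a hypersensitivity reaction (eg, urticaria, pruritus, angioedema, wheezing, dyspnea, or hypotension", and Section 7.1 describes one severe form as "a hypersensitivity reaction resulting in bronchospasm, wheezing and/or dyspnea that requires ventilatory support".

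**The concern.** A reader of the safety report will take a table with hypersensitivity in its title as the incidence of hypersensitivity by treatment group. Under the rule in Appendix 7 it is the incidence of anaphylactic and anaphylactoid reactions, Type I hypersensitivity and serum sickness. These are different quantities. The gap is made up of the milder, non-anaphylactic reactions that are neither Type I by coding nor serum sickness.

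Hypersensitivity is a risk that the protocol names, and SAP Section 5.4.1.1 sets up the groups through Week 24 so that guselkumab can be set against placebo over similar follow-up. If the dedicated count is low because the search is narrow, the table could be read as reassurance that it does not give.

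**Working it through.** No power, alpha or event-rate figure is involved, so the check is a comparison of texts.

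**Step 1. Is the definition closed?** Section 5.4.3 points to Section 6.7, and Section 6.7 says that the table sets the criteria. The row for this category has no standardised query, no higher-level term, no case report form checkbox and no medical review. The serum sickness row adds two serum sickness terms and nothing else. No other SAP text widens the search. The five terms are therefore the whole definition.

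**Step 2. What do the five terms cover?** Four are anaphylactic or anaphylactoid. The fifth, Type I hypersensitivity, is a genuine hypersensitivity term.

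**Step 3. Trace possible reports through the rule.** The documents do not show how a given verbatim will be coded, so each case is stated by its coded term.

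| Event as coded | In the dedicated summary? | Where else it appears |
|---|---|---|
| One of the four anaphylactic or anaphylactoid terms | Yes | General tables; listing of anaphylactic reactions |
| Type I hypersensitivity | Yes | General tables |
| A hypersensitivity term other than Type I | No | General tables |
| Urticaria or angioedema, judged by the investigator to be hypersensitivity | No | General tables; related-event table if judged related |
| Local reaction flagged on the case report form as an injection-site reaction | Only if coded to one of the five terms | Injection-site reaction table |

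The third and fourth lines are the omission.

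**Step 4. Can the missing count be rebuilt from other tables?** Not exactly. The general tables count participants separately for each event. Someone with both urticaria and angioedema is counted once under each, so adding the two counts that person twice. The tables also cannot separate urticaria judged to be hypersensitivity from urticaria with another cause.

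**Step 5. How do neighbouring rows work?** Appendix 7 defines infections by a system organ class and active tuberculosis by a high-level term with one exclusion. Malignancy, opportunistic infections and hepatic disorders are defined by standardised queries, and venous thromboembolism by a long customised term list. Malignancy, tuberculosis, opportunistic infections and major cardiovascular events also have medical review. A grouped query with review is thus already part of this SAP's practice. The hypersensitivity row has neither.

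**The case against.** The strongest reply is that a specific term list is a legitimate choice and that little is lost.

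- The protocol does not require this table. Its adverse events of special interest are malignancy and active tuberculosis (Section 8.3.6), and Section 9.4.4 asks for adverse events, serious adverse events, infections and injection-site reactions. The SAP goes beyond this.
- The narrow scope fits the protocol's emphasis. The supporting data in Table 1 concern serious reactions including anaphylaxis, and earlier results in Section 2.2.1.1.3 are reported as anaphylaxis or serum sickness.
- The events stay in the overall tables and, where they qualify, in the serious, severe, related, discontinuation and dose-interruption tables.
- No formal safety comparison is planned (SAP Section 5.4).

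All of this stands, and it limits the point to one descriptive table. It does not make the title match the content, and it does not supply a per-participant hypersensitivity count.

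Two stronger readings are tempting and are not supported. A reader might infer that the search holds anaphylaxis terms only. It does not, because Type I hypersensitivity is on the list. A reader might also set the six signs in Protocol Section 8.2.10 against the five terms, find no overlap, and call the search empty for hypersensitivity. That compares bedside signs with coded diagnoses. Section 8.2.10 is an instruction to observe participants and does not define an analysis category. Section 10.6.5 asks investigators to record a diagnosis, where they can, when symptoms share a cause. Pruritus, dyspnea and hypotension are nonspecific, and pruritus especially so in a trial that enrols people with psoriasis. The absence of overlap is therefore not a measure of the under-count.

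**Conclusion.** The point holds in a limited form. As written, the SAP will report under a hypersensitivity label a count that its own rule confines to five preferred terms plus the two serum sickness terms. Non-anaphylactic hypersensitivity reactions coded elsewhere are omitted from that count.

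The size of the omission cannot be given. It depends on how many such reactions occur and how they are coded, and the documents give neither. The conclusion rests on one assumption: that at least some reactions regarded as hypersensitivity will be coded outside the five terms. If none are, the label is still too broad but no event is missed.

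A reader might go further and infer that the table will show zero, that events will disappear from the report, or that participants are less well protected. The documents support none of these. The events remain in the general tables, and clinical handling follows the protocol and does not depend on this search. Efficacy, type I error and sample size are not affected. This is a cheap improvement to one safety table.

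**What to change.** Either of two changes is enough.

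1. **Match the label to the search.** Retitle the Section 5.4.3 summary and the Appendix 7 row to say what is counted, for example *Anaphylaxis and Type I hypersensitivity*, with serum sickness kept as its own part of the summary, and list the five terms in a footnote. This changes titles and a footnote only.
2. **Match the search to the label.** Keep the five-term row under that narrower name and add a separate *Hypersensitivity* row defined by a wider grouped query with medical review, as Appendix 7 already does for malignancy and opportunistic infections. Report the number of participants with at least one confirmed event. This costs one appendix row, minor programming and reviewer time. A wider query will also pick up unrelated events, which the medical review has to remove. The review should be done blind to treatment assignment, with its rules written down before the Week 24 unblinding.

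The second option gives the count that the present title promises. The first removes the misleading label at almost no cost.

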6.8. Appendix 8: Medications of Special Interest

Concomitant medications of special interest are defined as follows:

Concomitant Medication Special Interest Category	Categories
Other biologic	
treatments or other	
experimental treatments	
Non-biologic DMARD	MTX, SSZ, LEF, HCQ, chloroquine, gold preparations, penicillamine, other non-
_	biologic DMARDs
Oral corticosteroids	Oral corticosteroids
NSAIDs	NSAIDs

Prior Medication	
Special Interest	
Category	Categories
Prior anti-TNF agents	
Non-biologic DMARD	MTX, SSZ, LEF, HCQ, chloroquine, gold preparations, penicillamine, other non-
	biologic DMARDs
Immunosuppressives	Cyclosporine, azathioprine, mycophenolate mofetil, tacrolimus, other
	immunosuppressives
Systemic corticosteroids	Systemic corticosteroids
NSAIDs	NSAIDs
Apremilast	Apremilast
Previous medications	Non-biologic DMARDs, immunosuppressives, apremilast, systemic corticosteroids,
and therapies for PsA	NSAIDs
Previous medications	
and therapies for PsO	Cyclosporine, Topical, Acitretin, UVB, Apremilast, PUVA

6.9. Appendix 9: Laboratory Toxicity Grading

The grading scale use for lab assessments is based on CTCAE v5.0.

If a laboratory value falls within the grading as specified below but also within the local laboratory normal limits, the value is considered to be normal and will be reset to grade 0.

Pre-baseline measurements will use the same grading ranges as applied to baseline measurements. In case a test has two sets of ranges — one for baseline normal and one for baseline abnormal, the one for baseline normal will be applied for all measurements taken pre-baseline and on baseline.

Text in gray italic in the table is present in the grading scale but is not applied by Janssen when grading lab data.

CTCAE Term	Grade 1	Grade 2	Grade 3	Grade 4	Janssen implementation notes
Blood and lymphatic syst	em disorders	•		•	•
Anemia	Hemoglobin (Hgb) <lln -="" 10.0="" 100="" 6.2="" <lln="" dl;="" g="" l;="" l<="" mmol="" td="">Hemoglobin (Hgb) <10.0 - 8.0 g/dL; <6.2 - 4.9 mmol/L; <100 - 80g/L	Hemoglobin (Hgb) <8.0 g/dL; <4.9 mmol/L; <80 g/L; transfusion indicated	Life-threatening consequences; urgent intervention indicated	Clinical signs and symptoms are not taken into consideration for grading.	</lln>	Hemoglobin (Hgb) <10.0 - 8.0 g/dL; <6.2 - 4.9 mmol/L; <100 - 80g/L	Hemoglobin (Hgb) <8.0 g/dL; <4.9 mmol/L; <80 g/L; transfusion indicated	Life-threatening consequences; urgent intervention indicated	Clinical signs and symptoms are not taken into consideration for grading.
Leukocytosis	-	-	>100,000/mm ³ ; >100 x 10e ⁹ /L	Clinical manifestations of leucostasis; urgent intervention indicated	Clinical signs and symptoms are not taken into consideration for grading; Added ranges in SI unit (x 10e ⁹ /L).
Investigations					
Activated partial thromboplastin time prolonged	>ULN - 1.5×ULN	>1.5 - 2.5×ULN	>2.5×ULN; bleeding	-	Clinical signs and symptoms are not taken into consideration for grading.
Alanine aminotransferase increased	>ULN - 3.0×ULN if baseline was normal; 1.5 - 3.0×baseline if baseline was abnormal	>3.0 - 5.0×ULN if baseline was normal; >3.0 - 5.0×baseline if baseline was abnormal	>5.0 - 20.0×ULN if baseline was normal; >5.0 - 20.0×baseline if baseline was abnormal	>20.0×ULN if baseline was normal; >20.0×baseline if baseline was abnormal	Ranges defined for "abnormal baseline" are applied only if baseline >ULN. If baseline <lln, "normal="" applied.<="" are="" baseline"="" for="" ranges="" td="" then=""></lln,>
Alkaline phosphatase increased	>ULN - 2.5×ULN if baseline was normal; 2.0 - 2.5×baseline if baseline was abnormal	>2.5 - 5.0×ULN if baseline was normal; >2.5 - 5.0×baseline if baseline was abnormal	>5.0 - 20.0×ULN if baseline was normal; >5.0 - 20.0×baseline if baseline was abnormal	>20.0×ULN if baseline was normal; >20.0×baseline if baseline was abnormal	Ranges defined for "abnormal baseline" are applied only if baseline >ULN. If baseline <lln, "normal="" applied.<="" are="" baseline"="" for="" ranges="" td="" then=""></lln,>
Aspartate aminotransferase increased	>ULN - 3.0×ULN if baseline was normal; 1.5 - 3.0×baseline if baseline was abnormal	>3.0 - 5.0×ULN if baseline was normal; >3.0 - 5.0×baseline if baseline was abnormal	>5.0 - 20.0×ULN if baseline was normal; >5.0 - 20.0×baseline if baseline was abnormal	>20.0×ULN if baseline was normal; >20.0×baseline if baseline was abnormal	Ranges defined for "abnormal baseline" are applied only if baseline >ULN. If baseline <lln, for<="" ranges="" td="" then=""></lln,>

 $\label{eq:confidential} \textbf{CONFIDENTIAL} - \textbf{FOIA} \ \textbf{Exemptions} \ \textbf{Apply} \ \textbf{in} \ \textbf{U.S.}$

CTCAE Term	Grade 1	Grade 2	Grade 3	Grade 4	Janssen implementation notes
					"normal baseline" are applied.
Blood bilirubin increased	>ULN - 1.5×ULN if baseline was normal; >1.0 - 1.5×baseline if baseline was abnormal	>1.5 - 3.0×ULN if baseline was normal; >1.5 - 3.0×baseline if baseline was abnormal	>3.0 - 10.0×ULN if baseline was normal; >3.0 - 10.0×baseline if baseline was abnormal	>10.0×ULN if baseline was normal; >10.0×baseline if baseline was abnormal	Ranges defined for "abnormal baseline" are applied only if baseline >ULN. If baseline <lln, "normal="" applied.<="" are="" baseline"="" for="" ranges="" td="" then=""></lln,>
CD4 lymphocytes decreased	<lln -="" 500="" mm3; <lln -="" 0.5×10e9 /L</lln></lln>	<500 - 200/mm ³ ; <0.5 - 0.2×10e ⁹ /L	<200 - 50/mm ³ ; <0.2 - 0.05×10e ⁹ /L	<50/mm ³ ; <0.05×10e ⁹ /L	
Cholesterol high	>ULN - 300 mg/dL; >ULN - 7.75 mmol/L	>300 - 400 mg/dL; >7.75 - 10.34 mmol/L	>400 - 500 mg/dL; >10.34 - 12.92 mmol/L	>500 mg/dL; >12.92 mmol/L	
CPK increased	>ULN - 2.5×ULN	>2.5×ULN - 5×ULN	>5×ULN - 10×ULN	>10×ULN	
Creatinine increased	Creatine Kinase >ULN - 1.5×ULN	Creatine Kinase >1.5 - 3.0×baseline; >1.5 - 3.0×ULN	Creatine Kinase >3.0×baseline; >3.0 - 6.0×ULN	Creatine Kinase >6.0×ULN	
Fibrinogen decreased	<1.0 - 0.75×LLN; if abnormal, <25% decrease from baseline	<0.75 - 0.5×LLN; if abnormal, 25% - <50% decrease from baseline	<0.5 - 0.25 x LLN; if abnormal, 50% - <75% decrease from baseline	<0.25×LLN; if abnormal, 75% decrease from baseline; absolute value <50 mg/dL	Ranges defined for "abnormal" are applied only on values <lln. 0="" assigned="" be="" grade="" to="" values="" will="">ULN.</lln.>
GGT increased	>ULN - 2.5×ULN if baseline was normal; 2.0 - 2.5×baseline if baseline was abnormal	>2.5 - 5.0×ULN if baseline was normal; >2.5 - 5.0×baseline if baseline was abnormal	>5.0 - 20.0×ULN if baseline was normal; >5.0 - 20.0×baseline if baseline was abnormal	>20.0×ULN if baseline was normal; >20.0×baseline if baseline was abnormal	Ranges defined for "abnormal baseline" are applied only if baseline >ULN. If baseline <lln, "normal="" applied.<="" are="" baseline"="" for="" ranges="" td="" then=""></lln,>
Haptoglobin decreased	<lln< td="">-	-	-		</lln<>	-	-	-	
Hemoglobin increased	Increase in >0 - 2 g/dL; Increase in >0 - 20 g/L	Increase in >2 - 4 g/dL; Increase in >20 - 40 g/L	Increase in >4 g/dL; Increase in >40 g/L	-	The increase indicates the level of increase above normal (above ULN). Applied as, eg grade 1 (g/dL): >ULN – ULN+2 g/dL; Added ranges in SI unit (g/L).

 $\label{eq:confidence} \textbf{CONFIDENTIAL} - \textbf{FOIA Exemptions Apply in U.S.}$

CTCAE Term	Grade 1	Grade 2	Grade 3	Grade 4	Janssen implementation notes
INR increased	>1.2 - 1.5; >1 - 1.5 × baseline if on anticoagulation; monitoring only indicated	>1.5 - 2.5; >1.5 - 2.5 × baseline if on anticoagulation; dose adjustment indicated	>2.5; >2.5×baseline if on anticoagulation; bleeding	-	Concomitant therapy or clinical signs and symptoms are not taken into consideration for grading.
Lipase increased	>ULN - 1.5×ULN	>1.5 - 2.0×ULN; >2.0 - 5.0×ULN and asymptomatic	>2.0 - 5.0×ULN with signs or symptoms; >5.0×ULN and asymptomatic	>5.0×ULN and with signs or symptoms	"Asymptomatic" ranges are not taken into consideration for grading, ie worst case grading is applied.
Lymphocyte count decreased	<lln -="" 800="" mm3; <lln -="" 0.8="" 10e9/L</lln></lln>	<800 - 500/mm ³ ; <0.8 - 0.5×10e ⁹ /L	<500 - 200/mm ³ ; <0.5 - 0.2×10e ⁹ /L	<200/mm ³ ; <0.2×10e ⁹ /L	
Lymphocyte count increased	-	>4000/mm ³ - 20,000/mm ³ ; >4 - 20×10e ⁹ /L	>20,000/mm ³ ; >20×10e ⁹ /L	-	Added ranges in SI unit (×10e ⁹ /L).
Neutrophil count decreased	<lln -="" 1500="" mm3; <lln -="" 1.5×10e9 /L</lln></lln>	<1500 - 1000/mm ³ ; <1.5 - 1.0×10e ⁹ /L	<1000 - 500/mm ³ ; <1.0 - 0.5×10e ⁹ /L	<500/mm ³ ; <0.5×10e ⁹ /L	Both Neutrophils and segmented neutrophils are graded using these criteria.
Platelet count decreased	<lln -="" 75,000="" mm3; <lln -="" 75.0×10e9 /L</lln></lln>	<75,000 - 50,000/mm ³ ; <75.0 - 50.0×10e ⁹ /L	<50,000 - 25,000/mm ³ ; <50.0 - 25.0×10e ⁹ /L	<25,000/mm ³ ; <25.0×10e ⁹ /L	
Serum amylase increased	>ULN - 1.5×ULN	>1.5 - 2.0×ULN; >2.0 - 5.0×ULN and asymptomatic	>2.0 - 5.0×ULN with signs or symptoms; >5.0×ULN and asymptomatic	>5.0×ULN and with signs or symptoms	"Asymptomatic" ranges are not taken into consideration for grading, ie worst case grading is applied.
White blood cell decreased	<lln -="" 3000="" mm3; <lln -="" 3.0×10e9 /L</lln></lln>	<3000 - 2000/mm ³ ; <3.0 - 2.0×10e ⁹ /L	<2000 - 1000/mm ³ ; <2.0 - 1.0×10e ⁹ /L	<1000/mm ³ ; <1.0×10e ⁹ /L	
Metabolism and nutrition	ı disorders				
Acidosis	pH <normal, but="">=7.3</normal,>	-	pH <7.3	Life-threatening consequences	pH <normal <lln.="" and="" are="" as="" clinical="" consideration="" for="" grading.<="" implemented="" into="" is="" not="" ph="" signs="" symptoms="" taken="" td=""></normal>

CTCAE Term	Grade 1	Grade 2	Grade 3	Grade 4	Janssen implementation notes
Alkalosis	pH >normal, but <=7.5	-	pH >7.5	Life-threatening consequences	pH >normal is implemented as pH >ULN. Clinical signs and symptoms are not taken into consideration for grading.
Hypercalcemia	Corrected serum calcium of >ULN - 11.5 mg/dL; >ULN - 2.9 mmol/L;	Corrected serum calcium of >11.5 - 12.5 mg/dL; >2.9 - 3.1 mmol/L;	Corrected serum calcium of >12.5 - 13.5 mg/dL; >3.1 - 3.4 mmol/L;	Corrected serum calcium of >13.5 mg/dL; >3.4 mmol/L;	Clinical signs and symptoms are not taken into consideration for grading.
	Ionized calcium >ULN - 1.5 mmol/L	Ionized calcium >1.5 - 1.6 mmol/L; symptomatic	Ionized calcium >1.6 - 1.8 mmol/L; hospitalization indicated	Ionized calcium >1.8 mmol/L; life-threatening consequences	
Hyperkalemia	Potassium >ULN - 5.5 mmol/L	Potassium >5.5 - 6.0 mmol/L; intervention initiated	Potassium >6.0 - 7.0 mmol/L; hospitalization indicated	Potassium >7.0 mmol/L; life-threatening consequences	Clinical signs and symptoms are not taken into consideration for grading.
Hypermagnesemia	Magnesium >ULN - 3.0 mg/dL; >ULN - 1.23 mmol/L	-	Magnesium >3.0 - 8.0 mg/dL; >1.23 - 3.30 mmol/L	Magnesium >8.0 mg/dL; >3.30 mmol/L; life-threatening consequences	Clinical signs and symptoms are not taken into consideration for grading.
Hypernatremia	Sodium >ULN - 150 mmol/L	Sodium >150 - 155 mmol/L; intervention initiated	Sodium >155 - 160 mmol/L; hospitalization indicated	Sodium >160 mmol/L; life-threatening consequences	Clinical signs and symptoms are not taken into consideration for grading.
Hypertriglyceridemia	Triglycerides 150 mg/dL - 300 mg/dL; 1.71 mmol/L - 3.42 mmol/L	Triglycerides >300 mg/dL - 500 mg/dL; >3.42 mmol/L - 5.7 mmol/L	Triglycerides >500 mg/dL – 1000 mg/dL; >5.7 mmol/L - 11.4 mmol/L	Triglycerides >1000 mg/dL; >11.4 mmol/L; life-threatening consequences	Clinical signs and symptoms are not taken into consideration for grading.
Hypoalbuminemia	Albumin <lln -="" 3="" dl;
<lln -="" 30="" g="" l<="" td="">Albumin <3 - 2 g/dL; <30 - 20 g/L	Albumin <2 g/dL; <20 g/L	Life-threatening consequences; urgent intervention indicated	Clinical signs and symptoms are not taken into consideration for grading.	</lln></lln>	Albumin <3 - 2 g/dL; <30 - 20 g/L	Albumin <2 g/dL; <20 g/L	Life-threatening consequences; urgent intervention indicated	Clinical signs and symptoms are not taken into consideration for grading.

CONFIDENTIAL – FOIA Exemptions Apply in U.S.

CTCAE Term	Grade 1	Grade 2	Grade 3	Grade 4	Janssen implementation notes
Hypocalcemia	Corrected serum calcium of <lln -="" 1.0="" 2.0="" 8.0="" <lln="" calcium="" dl;="" ionized="" l;="" l<="" mg="" mmol="" td="">Corrected serum calcium of <8.0 - 7.0 mg/dL; <2.0 - 1.75 mmol/L; Ionized calcium <1.0 - 0.9 mmol/L;	Corrected serum calcium of <7.0 - 6.0 mg/dL; <1.75 - 1.5 mmol/L; Ionized calcium <0.9 - 0.8 mmol/L;	Corrected serum calcium of <6.0 mg/dL; <1.5 mmol/L; Ionized calcium <0.8 mmol/L;	Clinical signs and symptoms are not taken into consideration for grading.	</lln>	Corrected serum calcium of <8.0 - 7.0 mg/dL; <2.0 - 1.75 mmol/L; Ionized calcium <1.0 - 0.9 mmol/L;	Corrected serum calcium of <7.0 - 6.0 mg/dL; <1.75 - 1.5 mmol/L; Ionized calcium <0.9 - 0.8 mmol/L;	Corrected serum calcium of <6.0 mg/dL; <1.5 mmol/L; Ionized calcium <0.8 mmol/L;	Clinical signs and symptoms are not taken into consideration for grading.
		symptomatic	hospitalization indicated	life-threatening consequences	
Hypoglycemia	Glucose <lln -="" 55="" dl;
<lln -="" 3.0="" l<="" mmol="" td="">Glucose <55 - 40 mg/dL; <3.0 - 2.2 mmol/L	Glucose <40 - 30 mg/dL; <2.2 - 1.7 mmol/L	Glucose <30 mg/dL; <1.7 mmol/L; life-threatening consequences; seizures	Clinical signs and symptoms are not taken into consideration for grading. Urine glucose is not graded.	</lln></lln>	Glucose <55 - 40 mg/dL; <3.0 - 2.2 mmol/L	Glucose <40 - 30 mg/dL; <2.2 - 1.7 mmol/L	Glucose <30 mg/dL; <1.7 mmol/L; life-threatening consequences; seizures	Clinical signs and symptoms are not taken into consideration for grading. Urine glucose is not graded.
Hypokalemia	Potassium <lln -="" 3.0="" l<="" mmol="" td="">Symptomatic with Potassium <lln -="" 3.0="" indicated<="" intervention="" l;="" mmol="" td="">Potassium <3.0 - 2.5 mmol/L; hospitalization indicated	Potassium <2.5 mmol/L; life-threatening consequences	"Symptomatic" ranges are applied for grade 2, grade 1 not assigned, ie worst case applied. Clinical signs and symptoms are not taken into consideration for grading of grade 3 and 4.	</lln>	</lln>	Symptomatic with Potassium <lln -="" 3.0="" indicated<="" intervention="" l;="" mmol="" td="">Potassium <3.0 - 2.5 mmol/L; hospitalization indicated	Potassium <2.5 mmol/L; life-threatening consequences	"Symptomatic" ranges are applied for grade 2, grade 1 not assigned, ie worst case applied. Clinical signs and symptoms are not taken into consideration for grading of grade 3 and 4.	</lln>	Potassium <3.0 - 2.5 mmol/L; hospitalization indicated	Potassium <2.5 mmol/L; life-threatening consequences	"Symptomatic" ranges are applied for grade 2, grade 1 not assigned, ie worst case applied. Clinical signs and symptoms are not taken into consideration for grading of grade 3 and 4.
Hypomagnesemia	Magnesium <lln -="" 1.2="" dl;
<lln -="" 0.5="" l<="" mmol="" td="">Magnesium <1.2 - 0.9 mg/dL; <0.5 - 0.4 mmol/L	Magnesium <0.9 - 0.7 mg/dL; <0.4 - 0.3 mmol/L	Magnesium <0.7 mg/dL; <0.3 mmol/L; life-threatening consequences	Clinical signs and symptoms are not taken into consideration for grading.	</lln></lln>	Magnesium <1.2 - 0.9 mg/dL; <0.5 - 0.4 mmol/L	Magnesium <0.9 - 0.7 mg/dL; <0.4 - 0.3 mmol/L	Magnesium <0.7 mg/dL; <0.3 mmol/L; life-threatening consequences	Clinical signs and symptoms are not taken into consideration for grading.
